|--|-----------|--|-------|-----------------|-------|---------|-------|---------|--------|---------|--------|---------|--------------------------|--------|---------------------------|--|
| | | Onset Period | | Efficacy Period | | | | | | | | | | EOT | EOS/ ET ^{a,b} | |
| | | Baseline | | Month 1 | | Month 2 | | Month 3 | | Month 4 | | Month 5 | | | | |
| Study Day (±Visit Window) | -60 to -1 | Day 1 | 15 ±3 | 29 ±7 | 43 ±3 | 57 ±7 | 85 ±7 | 113 ±7 | 141 ±7 | 169 ±7 | 197 ±7 | 225 ±7 | 253 ±7 | 281 ±7 | | |
| Haem-A-QOL / Haemo-QOL ^s | | X | | | | | | | | | | | X ^s | | | |
| HAL / pedHAL ^s | | X | | | | | | | | | | | X ^s | | | |
| TSQM-9 ^s | | X | | | | | | | | | | | X ^s | | | |
| Fitusiran Administration (Fitusiran arm only) | | X | | X | | X | X | X | X | X | X | X | | | | |
| Patient Education Module Training | | X | | | | | | | | | | | | | | |
| Bleed Management Review ^t | | Review with patient at each visit and contact every 2 weeks between visits | | | | | | | | | | | | | | |
| Bleeding Episodes/eDiary ^u | | Review with patient at each visit and contact every 2 weeks between visits | | | | | | | | | | | | | | |
| Perioperative Assessment ^v | | Continuous | | | | | | | | | | | | | | |
| Adverse Events ^w | | Continuous | | | | | | | | | | | | | | |
| Concomitant Medications ^x | | Continuous | | | | | | | | | | | | | | |

Abbreviations: AEs = adverse events; AT = antithrombin; ECG = electrocardiogram; eDiary = electronic diary; EOS = end of study; EOT = end of treatment; ET = early-termination; FVIII = factor VIII; FIX = factor IX; F/U = follow-up; Haem-A-QOL = Hemophilia Quality of Life Questionnaire for Adults; Haemo-QOL = Hemophilia Quality of Life Questionnaire for children and adolescents; HAL = Hemophilia Activities List; HJHS = Hemophilia Joint Health Score; IMP = Investigational medicinal product; Min = minute; pedHAL = pediatric HAL; PK = pharmacokinetics; TG = thrombin generation; TSQM-9 = Treatment Satisfaction Questionnaire for Medication

Note:

- See Section 7 for study assessment instructions.
- Any Screening assessments performed within 7 days prior to baseline do not need to be repeated at the Baseline visit.

- Rescreening of patients is permitted with consultation of the study Medical Monitor.
- Laboratory parameters are described in Section 7.5.5 and listed in Table 5.

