- As clinical research parameters TG, D-dimer, and all other non-safety laboratory parameter results will not be communicated to sites. AT and factor results will be provided at screening for confirmation of eligibility. AT results will be provided at AT F/U visits for monitoring.
- When scheduled at the same time points, vital signs and 12-lead ECGs will be performed before the physical examinations and blood/urine sample collections.
- Unless otherwise specified, assessments on dosing days are predose.

^a Not required at Early Termination Visit for patients who complete assessment at EOT Visit and subsequently Early Terminate.

^b Patients in the fitusiran treatment arm who discontinue IMP dosing for any reason and agree to complete the remaining assessments through the EOS/ET and AT FU visits may receive treatment consistent with local standard practice for their disease per Investigator judgment once AT activity levels return to ~60% (per the central laboratory) or per Investigator discretion in conjunction with consultation with the study Medical Monitor. For patients who withdraw from the study early and do not consent to complete remaining assessments through the EOS/ET and AT FU visits, every effort should be made to conduct the assessments performed at the EOS/ET visit.

^c Patients in the fitusiran treatment arm not enrolling in the extension study will complete AT F/U visits at monthly intervals following final fitusiran dose until AT activity level returns to ~60% (per the central laboratory) or per Investigator discretion in consultation with the study Medical Monitor.

^d The complete medical history/disease history (ie, including bleeding episode and treatment history over the prior 6 months) to be recorded at Screening.

^e Randomization may occur within 3 days prior to Day 1.

^f eDiary training will be completed at the Clinic at Screening (see Section 7.2.1).

^g A full physical exam will be performed at Screening only; a directed physical exam will be performed at all other visits (see Section 7.5.3).

^h Height will be recorded at Screening only. Weight will be recorded at all other visits (see Section 7.5.2).

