¹ 12-lead ECGs will be performed in triplicate. For patients on Fitusiran: On Day 1 and Month 7, 12-lead ECG will be performed predose and 4 hours (± 30 min) postdose (see Section 7.5.4). The Month 9 12-lead ECGs will be performed only in those patients who are performing the ET visit and may be performed in singlicate. For patients in the on-demand arm: On Day 1 and Month 7, two ECG measurements should be performed approximately 4 hours (± 30 min) apart.

^j Hepatitis C virus antibody positive patients only. FibroScan where available, otherwise FibroTest and APRI.

^k Sample may be used for study of biomarkers related to hemophilia and associated conditions, investigations of emerging safety issues, or the development of fitusiran. After specified analyses are run, residual samples may be stored for up to 15 years from last patient last visit, or as per local regulations, and used for further study of biomarkers related to hemophilia and associated conditions, investigation of emerging safety issues, or the development of fitusiran. Samples drawn from central lines may be excluded from TG analysis.

^l In addition to the specified time points, TG levels and AT levels will also be performed in East Asian patients at East Asian sites (defined as patients from sites in China, Japan, South Korea, and Taiwan) on Day 2 and Day 8.

^m Only for patients who do not enroll in the open-label extension study.

ⁿ For patients on the fitusiran arm, samples will be collected within 4 hours prior to dosing on dosing days.

^o Serum chemistry and hematology laboratory parameters will be collected as listed in Table 5.

^p Liver function tests (LFTs) and hepatic tests are as listed in Table 5. LFTs may be obtained up to 7 days before the clinic visit on which fitusiran dosing is scheduled. LFTs performed within 7 days of Day 1 will only be used to inform dosing on Day 1 and do not need to be used to confirm eligibility. LFTs can be analyzed locally, but if a local assessment is drawn, a serum chemistry sample must also be drawn for analysis at the central laboratory. Under conditions of elevated ALT and/or AST see Table 6 and Section 6.2.3.1. LFT results will be obtained prior to receiving monthly fitusiran dosing.

^q All patients will be tested for antibodies to fitusiran at the Screening visit. After randomization, testing for antibodies to fitusiran will be performed in the fitusiran treatment arm only.

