All patients will be treated for a total of 9 months; patients randomized to the fitusiran treatment arm will receive a total of 9 SC injections of fitusiran. Because the full PD effect of fitusiran is not achieved until approximately 28 days after receiving the first dose, efficacy will be assessed during the final 8 months on study (Day 29 to Month 9). Therefore, the overall fitusiran treatment period is defined as the onset period (Day 1 to Day 28 after receipt of the first dose, during which the AT lowering capacity of fitusiran is increasing but has not yet reached therapeutic levels) plus the efficacy period (Day 29 and after, when the AT lowering capacity of fitusiran has achieved therapeutic target range).

Patients may undergo unplanned or emergency surgery during the study, but must not schedule non-urgent surgery to occur during the study. Perioperative guidance should be followed as specified in Section 6.6.

A Study Steering Committee, composed of experts in the field of hemophilia, will advise the Sponsor on study design and conduct (see Section 4.6).

An independent data monitoring committee (DMC) will oversee the safety and overall conduct of this study as described in Section 4.7.

The study design schema is presented in Figure 1. Patients who complete the study may be eligible for an open-label extension study in which patients coming from both the fitusiran and the on-demand arms will be administered monthly SC doses of fitusiran.

Figure 1: Study Design

Abbreviations: HA/HB = hemophilia type A / hemophilia type B; R = randomized

^a On-demand factor concentrates as routinely prescribed by physician per local standard practice.

^b Fitusiran treatment arm patients who do not enroll in the extension study: AT activity level will be monitored at monthly intervals following the final fitusiran dose until activity levels return to approximately 60% (per the central laboratory) or per Investigator discretion in consultation with the study Medical Monitor.

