5.3.2. Withdrawal From Study

A patient or guardian may withdraw consent from study participation at any time. The Investigator may withdraw a patient at any time if this is considered to be in the patient's best interest. Any withdrawal from the study must be fully documented in the eCRF, and should be followed-up by the Investigator.

However, study integrity and interpretation is best maintained if all enrolled patients continue study assessments and follow-up even if study treatment is discontinued. Patients considering withdrawing from the study should be informed that they can discontinue treatment and still remain in the study to complete study assessments and follow-up as specified in the Schedule of Assessments (Table 1). If a patient still chooses to discontinue study treatment and withdraw from all follow-up, every effort should be made to conduct the EOS/ET assessments within 4 weeks of the last dose (see Table 1). When a patient withdraws from the study, the withdrawal of consent and the reason for withdrawal must be recorded in the appropriate section of the eCRF

and all efforts will be made to complete and report the observations as thoroughly as possible. There will be no replacements of patients who withdraw from this study.

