7.5.5.2. Immunogenicity

Blood samples will be collected to evaluate antidrug antibodies (ADAs) to fitusiran. Blood samples for ADA testing must be collected within 4 hours before IMP administration as specified in the Schedule of Assessments (Table 1). In addition, a blood sample to evaluate ADAs will be collected at the ET visit, if applicable.

Details regarding the processing, shipping, and analysis of the samples are provided in the Laboratory Manual.

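### Table 1 footnote a lets predose EOT assessments replace the early-termination assessments of a fitusiran patient dosed at EOT, contrary to footnote b and Section 5.3.2

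*Protocol*

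**What the plan says.** Four statements in the protocol bear on the same patient: one in the fitusiran arm who attends the EOT visit, is dosed there, and then leaves.

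- **Table 1, footnote a** (EOS/ET column header): "Not required at Early Termination Visit for patients who complete assessment at EOT Visit and subsequently Early Terminate".
- **Table 1, general notes:** "Unless otherwise specified, assessments on dosing days are predose". Footnote p adds, for liver function tests, "LFT results will be obtained prior to receiving monthly fitusiran dosing", and allows them up to 7 days before the dosing visit. Footnote n puts the AT and ADA samples within 4 hours before dosing.
- **Table 1, footnote b** (same header), for patients who withdraw early and do not agree to the remaining EOS/ET and AT follow-up assessments: "every effort should be made to conduct the assessments performed at the EOS/ET visit".
- **Section 5.3.2**, for patients who stop treatment and leave all follow-up: "every effort should be made to conduct the EOS/ET assessments within 4 weeks of the last dose".

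Section 7.5.5.2 adds that "a blood sample to evaluate ADAs will be collected at the ET visit, if applicable".

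**The concern.** Footnote a treats the EOT assessments as equivalent to those at the ET visit. That is reasonable if nothing happens between the two. For a fitusiran patient dosed at EOT, the last dose falls between them, so the earlier results say nothing about what follows it. Footnote a makes no exception for such a patient, and the passages that ask for the ET assessments make none for a patient who completed EOT. A site holding the protocol cannot tell which instruction governs.

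At stake is laboratory and examination follow-up of named risks. Section 1.5 lists thrombosis and liver transaminase abnormalities among the possible risks. Section 7.5.6.1 makes ALT or AST above 3 times ULN, and suspected thrombosis, events of special interest. Table 3 is written for patients with transaminase elevation and no symptoms, a finding that needs a blood test. Section 4.2 provides for up to 6 further months of AT monitoring, so the drug effect is expected to outlast Day 225.

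The analysis is touched too. SAP Section 5.10 defines the Endpoint visit as the last non-missing post-baseline value on or before EOS/ET. With the ET assessments waived and no unscheduled sample, that value would be the predose Day 225 result.

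**Working it through.** No power, alpha or sample-size figure is involved. The check is a count of Table 1, some date arithmetic, and a comparison of columns.

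**1. Is EOT the ninth dosing visit?** Section 4.1 says "patients randomized to the fitusiran treatment arm will receive a total of 9 SC injections of fitusiran". The dosing row of Table 1 has marks on Days 1, 29, 57, 85, 113, 141, 169, 197 and 225. That is nine marks, which reproduces the stated total and matches 1 + 28 × (k − 1) for k = 1 to 9, ending at 1 + 28 × 8 = 225. The ninth mark is in the EOT column, and there is none in the EOS/ET column (Day 253).

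**2. How long after the ninth dose is the EOS/ET visit?**
- Nominal: 253 − 225 = 28 days.
- Shortest with both ±7-day windows: (253 − 7) − (225 + 7) = 246 − 232 = 14 days.
- Longest: (253 + 7) − (225 − 7) = 260 − 218 = 42 days.
- The AT follow-up column (Day 281) is nominally 281 − 225 = 56 days after the dose.

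**3. Which assessments could the waiver remove, and does AT follow-up restore them?**

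| Assessment | EOT (Day 225) | EOS/ET (Day 253) | AT follow-up (Day 281) |
|---|---|---|---|
| LFTs, chemistry, hematology, coagulation | yes, predose | yes | yes |
| AT activity | yes, predose | yes | yes |
| Vital signs, directed examination | yes, predose | yes | yes |
| ADA | yes, predose | yes (not if entering the extension) | no |
| ECG | no | yes (ET patients only, footnote i) | no |
| Urinalysis | no | yes | no |

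Read item by item, footnote a waives the first four rows. It does not reach ECG or urinalysis, because they cannot have been completed at EOT.

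**4. Who is left without the data?**
- A patient who leaves after the EOT dose but attends AT follow-up regains the first three rows, later than planned, but has no scheduled ADA sample after the ninth dose.
- A patient who also declines AT follow-up has none of the four rows after the ninth dose if the site applies footnote a.
- If the site instead applies footnote b and Section 5.3.2, it tries to obtain all of them.
- On-demand patients, and fitusiran patients who stopped dosing before Day 225, receive no dose at EOT, so the waiver hides nothing that follows a dose at that visit.

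**The case against.** The strongest reply is that footnote a waives one visit and the protocol has other safeguards. Fitusiran patients not entering the extension are to attend monthly AT follow-up visits (footnote c), with examination, vital signs and safety laboratory tests. Adverse events are recorded through Follow-Up (footnote w), serious events are followed to resolution or stability, and events of special interest are reported within 24 hours. The patient who declines AT follow-up is the one whom the second sentence of footnote b and Section 5.3.2 address, so data are lost only if a site follows footnote a and sets both aside.

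Most of this stands, and it limits the size of the problem. It does not remove it. Footnote a is as specific as footnote b, sits on the same header, and nothing ranks one above the other. Event recording cannot find a silent transaminase rise without a test. AT follow-up carries no ADA sample, and Section 7.5.5.2 promises one at ET only if applicable, which does not settle whether the waiver applies.

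A reader might infer more than the documents support:

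- **That such a patient has no safety data after the last dose.** Event recording and AT follow-up contradict this for anyone still in contact, and read item by item the waiver leaves ECG and urinalysis due.
- **That every early leaver is affected.** Only fitusiran patients dosed at EOT are.
- **That the 20% drop-out assumption measures the group.** It is a whole-trial, two-arm planning figure (120 × 0.80 = 96 = 64 + 32) and does not describe exits after Day 225.
- **That post-dose abnormalities will be under-counted in the fitusiran arm.** That is possible, but no frequency is given from which to show it.

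**Conclusion.** The contradiction is real. As written, footnote a permits the ET assessments to be omitted after the ninth dose on the basis of predose results, while footnote b and Section 5.3.2 ask that they be attempted.

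The exposed group is fitusiran patients who are dosed at EOT, terminate before the EOS visit, and are seen at a site that follows footnote a. Within it, post-dose LFTs, chemistry, hematology, coagulation, AT, vital signs and the directed examination could be missed in those who also decline AT follow-up. ADA could be missed even in those who attend. The omitted visit would nominally fall 28 days after the dose (14 to 42 with both windows).

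The documents do not say how many patients this is. It is probably few, since the interval is short and comes at the end of treatment. The conclusion assumes that footnote a is read item by item; if it is read as waiving the whole visit, ECG and urinalysis are lost as well. No efficacy endpoint, estimand or sample-size figure changes.

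**What to change.** Reconcile footnote a with footnote b and Section 5.3.2. Either limit the waiver to patients who did not receive fitusiran at the EOT visit, or limit it to assessments done after the last dose. In both cases the EOS/ET safety assessments, including ADA, are then sought in patients dosed at EOT. The wording should ask for effort, as Section 5.3.2 does, because a patient who has withdrawn cannot be obliged to attend. Stating that the waiver applies item by item would also settle ECG and urinalysis.

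The cost is one footnote edit and, in a few patients, one visit's assessments that Section 5.3.2 already requests.

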4.5. Blinding

This study is an open-label study so blinding is not applicable; however, performing aggregate summaries of efficacy data by treatment arm will be restricted until database lock.

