5.2 General methods

All data listings that contain an evaluation date will contain a study day relative to the day of Day 1 visit when baseline assessments are performed and fitusiran first dose is given, which is designated as Day 1. The Day 1 visit date should coincide with randomization date but could occur within 3 days after the randomization. If the fitusiran first dose is given after Day 1 visit, a study day will be calculated relative to the day of first dose. Study days will be calculated as evaluation date – Day 1 visit date (or first dose date) + 1 and pre-Day 1 visit days will be calculated as evaluation date – Day 1 visit date (or first dose date). For example, the day prior to Day 1 visit will be Day –1 and the day after Day 1 visit will be Day 2, etc. There will be no Study Day 0.

Categorical variables will be summarized using counts and percentages. Continuous variables will be summarized using the number of patients (n), mean, SD, median, interquartile range (Q1, Q3), minimum value (min), and maximum value (max). The precision of the measurement for each continuous variable will be used to determine the number of decimal places to present in tables, figures and derived listings. Minimum and maximum values will be reported with the same precision as the units of measure. The other statistics will be reported to 1 greater decimal place, and the SD will be reported to 2 additional decimal places. Any values that require transformation to standard units (metric or SI) will be converted with the appropriate corresponding precision.

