5.5 Baseline definitions

Unless noted otherwise, baseline for on demand group will be defined as the last non-missing value on or before Day 1 visit. Baseline for fitusiran group is defined as the last non-missing value before 1st dose of fitusiran or the last non-missing value on or before randomization date for patients who were randomized but never exposed to fitusiran.

ECG measurements are taken in triplicate. For the on demand group, the average of the first triplicate readings on or before Day 1 visit or on screening visit will be used as baseline. For fitusiran group, the average of the last triplicate readings before 1st dose is used as baseline.

For questionnaire assessments, the last non-missing value on or before Day 1 visit will be used as baseline. For fitusiran patients, the last non-missing value on or before date of 1st dose of fitusiran or the last non-missing value on or before randomization date for patients who were randomized but never exposed to fitusiran will be used as baseline.

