6.3.2.4 Haem-A-QoL

The Haem-A-QoL will be provided to patients ≥ 17 years of age and includes 46 items contributing to 10 QoL domains (physical health, feelings, view of yourself, sports and leisure,

work and school, dealing with hemophilia, treatment, future, family planning, partnership and sexuality). Scoring for each item is based on a 5-point Likert scale (never, rarely, sometimes, often, and all the time), and higher scores represent greater impairment. The change from baseline in physical health score and total score of Haem-A-QoL at the end of the study will be analyzed using an analysis of covariance (ANCOVA) model with fixed effects of treatment arm, randomization strata of number of bleeding episodes in the 6 months prior to study entry (≤ 10 vs > 10) and randomization strata of hemophilia type (A vs B), baseline Haem-A-QoL physical health score and total score as covariates. Least square means of the physical health score and total score in each treatment arm and the difference of the least square means of the physical health score and total score in the two arms (along with the 95% CI and p-value) will be presented. The normality assumption based on ANCOVA model will be examined and a sensitivity analysis based on the non-parametric Wilcoxon-Mann-Whitney test will be performed. Domain scores, standardized scale scores, and transformed scale scores for Haem-A-QoL and their changes from baseline will be summarized. The above ANCOVA analysis is based on observed data. For patient with missing assessment due to early withdrawal, a sensitivity analysis will also be performed by imputing the domain score and total score as the worst score if the reason of withdrawal is treatment-related in the corresponding treatment arm, and as the average score for other reasons of withdrawal that are not treatment related in the corresponding treatment arm. The same analysis as main will be performed as a sensitivity analysis by excluding values of those who completed Haem-A-QoL at baseline after first dose of fitusiran.

To evaluate the impact of Covid-19, the same ANCOVA model will also be repeated on Covid-19 unaffected set. In addition, a sensitivity analysis using same ANCOVA model will be performed excluding the data impacted by Covid-19 major/critical protocol deviation. A supportive analysis will be repeated on the patients whose responses level to EQ-5D dimensions “anxiety/depression” is no change or improved from baseline.

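### Baseline Haem-A-QOL can be completed after open-label randomization, and no rule or planned analysis deals with patients already knowing their arm

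*Protocol*

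**What the plan says.** **Timing of randomization.** Table 1 marks randomization at Day 1, and footnote e adds: "Randomization may occur within 3 days prior to Day 1". SAP 5.2 agrees: "The Day 1 visit date should coincide with randomization date but could occur within 3 days after the randomization". Protocol 4.5 states: "This study is an open-label study so blinding is not applicable".

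**Timing of the questionnaires.** The Table 1 row for the quality-of-life instruments reads "Haem-A-QOL / Haemo-QOL ^s | | X": an empty Screening cell, then a first assessment at Day 1. HAL/pedHAL, EQ-5D, TSQM-9, HJHS and resource use follow the same pattern. Footnote s requires completion at the clinic, with follow-up at the end-of-study visit but not at early termination.

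**Order within the visit.** The one order rule that reaches these instruments is a Table 1 note: "Unless otherwise specified, assessments on dosing days are predose".

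**What counts as baseline.** SAP 5.5: "For questionnaire assessments, the last non-missing value on or before Day 1 visit will be used as baseline". For the treated arm it continues: "For fitusiran patients, the last non-missing value on or before date of 1st dose of fitusiran". The history table in SAP 2.6 records that version 2 moved the baseline anchor from randomization to the Day 1 visit.

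**Use.** Haem-A-QOL physical health and total score form step 5 of the hierarchy (Protocol 8.2.5, SAP 5.7). SAP 6.3.2.4 analyses change by ANCOVA with baseline as covariate. Its sensitivity analysis on baseline timing repeats the model "excluding values of those who completed Haem-A-QoL at baseline after first dose of fitusiran".

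**The concern.** ANCOVA on change gives a fair comparison when the baseline is a pre-randomization quantity, which randomization balances in expectation. A self-reported score given after a man learns that he will, or will not, receive the new drug is no longer such a quantity. If the news changes how he answers, the covariate itself carries an effect of allocation, and adjusting for it moves the treatment difference instead of correcting it.

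The SAP already treats baseline timing as an issue, but only in relation to the injection. For a questionnaire in an open-label trial, learning the allocation can matter before any dose is given, and it can matter in the on-demand arm, which the existing sensitivity analysis does not examine. At stake is the interpretation of two formally tested scores.

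**Working it through.** **1. Can the baseline follow randomization?**
- Randomized on Day -3 to Day -1: the first scheduled questionnaire is at Day 1, so it comes after randomization. The Table 1 note that Screening assessments within 7 days need not be repeated does not help, because no Screening questionnaire exists to carry forward.
- Randomized on Day 1: the order of questionnaire and interactive response system (IRS) call is open. The predose rule fixes the order relative to the injection only, and on-demand patients have no injection.
- Protocol 4.4 (the IRS call), 7.6.1 (questionnaires) and 7.6.3 (HJHS) do not supply the missing order.
- In the fitusiran arm the gap can exceed 3 days. SAP 5.2 allows a first dose after the Day 1 visit, and SAP 5.5 accepts values up to the first-dose date. The baseline rule therefore differs by arm.

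**2. How many patients does the tested endpoint involve?** About 120 randomized less about 10 adolescents under 18 (Protocol 4.3) is 110, plus any 17-year-olds. If the planned 20% drop-out falls evenly, 110 × 0.80 = 88 would have an end-of-study score. How many of them were randomized before Day 1, or were asked after the call, is not stated.

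**3. Size: illustration only.** The plan gives no figure on this point. Assumptions not found in the documents: baseline-outcome correlation r, equal unit SDs (so the slope equals r), a displacement d (in SD) of one arm's baseline, *no* displacement at follow-up, and no true effect. For sample size I use the plan's 32 and 64 evaluable patients, which is slightly generous given step 2.

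- Absolute bias in the adjusted difference = r × d; its sign is opposite to the shift.
- SE = √(1 − r²) × √(1/32 + 1/64) = √(1 − r²) × 0.2165.
- Type I error = 1 − Φ(1.96 − bias/SE) + Φ(−1.96 − bias/SE).

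| r | d | Bias (SD) | SE | Bias/SE | Type I error |
|---|---|---|---|---|---|
| 0.3 | 0.1 | 0.03 | 0.207 | 0.15 | 5.2% |
| 0.5 | 0.2 | 0.10 | 0.188 | 0.53 | 8.3% |
| 0.7 | 0.3 | 0.21 | 0.155 | 1.36 | 27% |

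Simulation with 20,000 replicates gave 8.4% for the middle row and 5.1% with d = 0.

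**4. Direction.** Higher scores mean greater impairment. If on-demand patients answer worse at baseline on learning their arm, the fitusiran benefit is understated. If fitusiran patients answer worse at baseline, it is overstated. The documents do not favour either.

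**5. What if the shift persists?** Patients also know their arm at Month 9. If the same shift d is present at both times, the bias is (1 − slope) × d with the current baseline and d with a pre-randomization baseline. Assuming a slope of 0.5 to 0.8 and a shift of 2 to 5 points, that is 0.2 × 2 = 0.4 to 0.5 × 5 = 2.5 points, against 2 to 5 points. The table above therefore covers one scenario only.

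**The case against.** The strongest reply is that the documents show a missing instruction, not an affected baseline. SAP 5.2 expects Day 1 and randomization to coincide, so the gap is meant to be the exception. The investigator or delegate makes the IRS call, and no passage says when the patient is told. Protocol Section 7 also refers to a Study Manual, not available here, which might set the order. All of this stands. A reader might infer that everyone randomized on Day -3 to Day -1 certainly answered knowing his arm, or that all 120 patients are affected. The documents support neither: they make knowledge possible, and Haem-A-QOL is not given below age 17.

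A second reply is that reach is limited. This also stands. Step 5 is last in the hierarchy, and the primary bleeding endpoint does not use this baseline. A reader might extend the ANCOVA argument to every change score, but TSQM-9, HAL/pedHAL, EQ-5D, HJHS and resource use are exploratory and only summarized. Haemo-QOL, also exploratory, is the one other instrument here with an ANCOVA. For HJHS, scored by a trained professional, the question is what the assessor knows.

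A third reply is that an earlier baseline does not cure open-label reporting, and under a persistent shift the adjusted difference can be further off. That is correct. It does not make the present rule preferable: with a pre-randomization baseline the remaining weakness lies in the follow-up score alone, where an open-label trial cannot avoid it. At present an unknown part may also lie in the covariate.

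**Conclusion.** The concern holds in a limited form. Following footnote e and SAP 5.5 as written can produce post-randomization Haem-A-QOL baselines in either arm. The ANCOVA cannot repair them, and the planned sensitivity analysis looks only at fitusiran values after the first dose.

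The frequency, direction and size of any bias cannot be determined from the documents. A reader might take the 5.2% to 27% range as the error rate of step 5. It is not: it rests on assumed correlations and shifts, and on a shift present at baseline and absent at follow-up. No sample-size or power figure changes. The point merits correction because the order is easy to specify and the endpoint is formally tested.

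**What to change.** **Protocol, Table 1 (footnotes e and s) and Section 7.6.** Require the baseline questionnaires, resource-use form and HJHS before the IRS call: at the Day 1 visit when randomization is that day, otherwise at a clinic visit before randomization such as Screening. Record completion and randomization times.

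**SAP 5.5, patients enrolled under the new rule.** Define questionnaire baseline as the last value before randomization, in both arms.

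**SAP 5.5 and 6.3.2.4, patients already enrolled.** Keep the current baseline, so that nobody randomized before Day 1 is left without one. Extend the Haem-A-QOL sensitivity analysis to both arms, excluding baselines completed after randomization, by date and, where recorded, by time. Date alone would miss a questionnaire completed later on the day of the call. If few pre-randomization values exist, compare baseline scores by arm and by days since randomization, and report the limitation. If enrolment has closed, only this part applies.

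**Cost.** Mostly a reordering of steps within a visit, a footnote and a few SAP sentences. Some questionnaires will come from patients who are then not randomized. A Screening baseline can be up to 60 days old. The sensitivity subset will be smaller than the main analysis.
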